This study will also explore the potential reduction of severe COVID-19 mediated disease through: 1) reducing time from symptom detection to treatment initiation (i.e., comparing treatment initiation times among those who test positive for COVID-19 in this study to published literature), and 2) closely monitoring COVID-19 symptoms among those who contract the virus (i.e., again, comparing participants in this study to published literature). COVID-19 is a novel virus and we do not fully understand its impact on our patient population. This study will provide useful, granular information about the daily symptoms of and recovery from COVID-19 in cancer patients. Data from this study will be used to pursue NIH R01 funding to formally evaluate the effects of using mHealth technology to monitor symptoms and health risk factors and intervene in real-time.

B. Background and Significance

The severe acute respiratory syndrome corona virus 2 (SARS-CoV-2) outbreak in late 2019 has resulted in approximately 4.28 million confirmed cases of novel coronavirus disease (COVID-19), with over 292,000 confirmed deaths worldwide (as of May 13, 2020)[1]. The United States has reported the greatest number of cases across the world, with a total of 1.4 million new cases and over 83,000 attributable deaths as of May 13, 2020. Severe disease accounts for approximately 10% of cases and adds tremendous burden on limited medical resources and medical personnel.

Risk factors for severe disease are largely unknown, but clinical experience suggests that persons over age 65 with co-morbid conditions, such as immunosuppression from cancer or chemotherapy, place cancer patients in the “high-risk” group for severe manifestations of COVID-19 mediated disease [2]. Therefore, cancer patients are likely at increased risk for COVID-19 infection and may have a poorer prognosis. According to recent data, the risk of severe infection in cancer patients approaches 40% with up to a 20% mortality rate [3]. Thus, there is increased need for invasive ventilation and intensive care unit admission to circumvent rapid clinical deterioration in this population. Novel methods are needed to remotely monitor for SARS-CoV-2 infection and rapidly intervene to reduce morbidity and mortality in cancer patients exhibiting symptoms of the virus. Given evidence of poor outcomes in cancer patients, early intervention may significantly improve outcomes.

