As a practicing oncologist within Stephenson Cancer Center, [name], Ph.D. is knowledgeable about the medical needs of the population that is being recruited for this study, and she regularly uses evidenced-based interventions to treat cancer. Her research and clinical experience complement [name] experience with research using mobile technology for health improvement. Additional study investigators include [name] (biostatistician) and [name] (basic and translational scientist) have agreed to assist with study recruitment and follow-up procedures.

D. Research Design and Methods

Study Design: A total of 500 treatment-seeking males and females will be asked to complete daily monitoring of symptoms and weekly monitoring of health risk factors weekly via smartphone app (Aim 1). Those who screen positive for COVID-19 will be triaged to emergency or non-emergency medical treatment. COVID-19 positive patients identified for non-emergent medical treatment will receive a study-supplied device to measure their oxygen level and heart rate and be instructed in the device's use. They will be prompted to enter vital signs data daily (such as body temperature, oxygen level, and heart rate) and questions from the app will change to assess the severity of COVID-19 related symptoms and inform changes in level of care, to emergency or non-emergency medical management as indicated by self-reporting. The proposed study will assess the impact of heightened symptom and vital sign monitoring on the early identification of severe manifestations of COVID-19 in this high-risk population (Aim 2). It is hypothesized that this will significantly improve COVID-19 related morbidity and mortality compared to the national and international rates currently reported in the literature. Figure 1 displays the participant flow through this 24-week study.

The SCC mHealth Shared Resource has created the versatile and reusable Insight™ mHealth Platform. Insight™ is HIPAA compliant and data are encrypted within the app. There will be 4 sources of data for the current study: 1) in-person data collected in a private room at the SCC

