When participants provide a pattern of responses that are suggestive of heightened risk for COVID-19 (See algorithm in Appendix), they will receive a suggestion to contact SCC staff, and the app will send an encrypted email containing this information to [name] and other SCC staff with a request to contact the participant to assess symptoms (see Appendix) and whether urgent medical attention is indicated. Should urgent medical attention be warranted, the patient will be instructed to the clinical unit most appropriate to the symptoms they reported through the app algorithm or discussed with the clinical nursing or physician staff. Non-emergent patients who screen positive for COVID-19 will begin an enhanced symptom and vital sign monitoring period that will continue until the participant reports that they are no longer symptomatic and/or a medical professional informs them that they no longer need to self-quarantine, which is expected to be approximately 21 days. These patients will receive a pulse oximeter (provided by the study) and the app questions will change to include daily prompts requesting that the patient input morning vital signs (temperature, heart rate, blood oxygen levels (SpO2)) and answer questions specific to the severity of symptoms and/or emergence of new symptoms of COVID-19. If a patient is hospitalized, they can continue to complete the daily assessments if they are willing and able to do so. The app will also support check-ins with SCC staff and after-hours medical staff as needed after diagnosis of COVID-19 or until the patient has been medically released from self-quarantine. Once the participants have completed the enhanced symptom and vital sign monitoring portion of the study, the pulse oximeter will be returned to the research team at the time of their next scheduled appointment. These devices will then be sterilized with both alcohol-based sanitizing products as well as ultraviolet light exposure in accordance with practices endorsed by the Centers for Disease Control.

Participants will continue to use the app to complete a final 24-week follow-up survey and will be contacted by phone (or RedCap if a medical condition prevents them from being able to speak for long periods of time) to complete a brief qualitative interview 24 weeks after study enrollment. Relevant demographic, cancer-specific and COVID-19 related data will be extracted

from electronic health records at the conclusion of the study.

E. Chart Review

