Beyond the above noted issues, the following step will be taken to minimize the likelihood of an adverse reaction to the study: The consent form will clearly describe the nature of the assessments and intervention. Thus, participants who feel uncomfortable with such assessments or intervention programs are not likely to agree to participate.

Potential Benefits. Potential benefits to participants include the use of study phones during the intervention period (at the current time, this benefit is estimated to be unlimited voice and text messages and 2 GB high speed data for the duration of their involvement in the study [i.e., 24 weeks]). Participants may also directly benefit from early detection of and immediate intervention upon presentation of COVID-19 symptoms. Finally, participants may also benefit from the enhanced symptom monitoring that is proposed.

Risks in Relation to Benefits. The current study involves very minimal risk to participants, and the risks of study participation are similar to that of participation in standard care (e.g., loss of confidentiality). All participants will be already seeking standard care before they are provided with any information about the research study. In addition, the knowledge gained from this study may be utilized to improve our understanding of symptom monitoring, health risk factors, and general experiences of individuals who undergo chemotherapy treatments to treat cancer.

We do not anticipate harm to research participants, but the principal investigators will monitor unanticipated problems (including serious and non-serious adverse events) and protocol deviations. Potential unanticipated problems for this project are all non-medical in nature. Unanticipated problems will be submitted within five University business days to the IRB using the Unanticipated Problem Report Form. The following information will be included in an adverse event report: date of event, attribution to data collection, and outcome of adverse events. All adverse events will also be reported in the annual report to the IRB along with a Summary of Participant Harms.

L. Multiple Sites

This is a single-site study.

M. Statistical Methods

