Aim 2. We will examine participant characteristics among those who are and are not transitioned to an Aim 2 monitoring of vital signs and severity of COVID-19 symptoms. We will also examine participant characteristics and outcomes for those that require emergent intervention versus non-emergent intervention. Among those who undergo enhanced monitoring, we will use descriptive statistics to summarize the proportion of patients experiencing the following outcomes: manifestations of severe disease, treatment related toxicity, need for hospitalization, and COVID-19 related mortality. We will also compare outcomes and tolerability of enhanced self-monitoring for severe infection and compare rates of disease related morbidity and mortality to baseline rates published in the literature. We will evaluate participant satisfaction with the app and identify ways to improve this novel patient monitoring technology. We will perform logistic regression to determine the odds of experiencing primary outcomes, based upon baseline characteristics (e.g., sex, race/ethnicity, cancer stage/type). Kaplan-Meier survival curves and log-rank tests of homogeneity will be used to identify the survival functions, describing the time to resolution of symptoms based upon

demographic characteristics. Because COVID-19 is a novel virus and we do not fully understand its impact on our patient population, this study will provide useful, granular information about the daily symptoms of and recovery from COVID-19 in cancer patients.

Aim 3. No analyses proposed, as this is a collaboration aim.

N. Data and Safety Monitoring Plan

Data quality and integrity will be held to the highest standard to ensure accurate reporting and documentation of the objectives outlined in the proposal. The Institutional Review Board and the Office of Clinical Research will monitor data and safety monitoring. The institutional plan for data and safety monitoring for all trials funded by the NCI has been adopted by the University and will be utilized for conduct of our planned proposal.

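### Comparing per-case COVID-19 severity and mortality with published rates could show an improvement that the app did not cause, because daily symptom prompting is likely to enlarge the case denominator with mild infections

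*Combined protocol and SAP*

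**What the plan says.** Section D, Study Design, hypothesises that heightened symptom and vital-sign monitoring will "significantly improve COVID-19 related morbidity and mortality compared to the national and international rates currently reported in the literature". Section A (Aim 2b) and section M (Aim 2) both plan to "compare rates of disease related morbidity and mortality to baseline rates published in the literature".

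Section M takes the outcome proportions per case: "Among those who undergo enhanced monitoring, we will use descriptive statistics to summarize the proportion of patients experiencing the following outcomes". Under Study application, entry to that group is described so: "Non-emergent patients who screen positive for COVID-19 will begin an enhanced symptom and vital sign monitoring period".

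The only cancer-specific benchmark is in section B: "the risk of severe infection in cancer patients approaches 40% with up to a 20% mortality rate". The Abstract and section B also give about 10% severe disease among COVID-19 cases overall.

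Every participant has the app; there is no control group. All are prompted once a day for 24 weeks and can report new symptoms between prompts. "When participants provide a pattern of responses that are suggestive of heightened risk for COVID-19", the app advises contacting the clinic and emails staff to follow up. Section K lists the detection effect as a benefit: "Participants may also directly benefit from early detection of and immediate intervention upon presentation of COVID-19 symptoms".

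No section states a test, alpha or decision rule for the literature comparison, how the published cases were found, a rate per enrolled participant, or a caveat about differences in ascertainment.

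**The concern.** A tool intended to find infections early is to be judged on a rate whose denominator is the infections found. If the app brings in mild cases that would otherwise have gone undiagnosed, the proportion with severe disease or death drops although no patient fares better, and it drops further the more thorough the screening.

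Naming one matched cancer series, or confirming every positive by test, would not remove this unless that series also came from daily symptom surveillance. A per-case rate below the literature therefore cannot separate better outcomes from more complete detection of mild illness, yet the hypothesis in section D would credit the difference to monitoring.

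**Working it through.** The plan gives no power or sample-size calculation for this comparison, so there is no figure to reproduce. The check asks what the comparison would show if the app had no effect.

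**Inputs from the protocol:** benchmark p0 = 40% severe and 20% mortality (section B, where they are worded as approached and as an upper limit; treated here as fixed); 500 participants.

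**Assumptions, none in the documents:**
- k = extra mild cases found per usually diagnosed case, with no severe outcome or death among them; range 0.25 to 1.
- n = total cases: 25, 50 or 100 (5%, 10% or 20% of 500), with about 10 as a low case.
- Exact binomial test of the observed rate against p0, one-sided 0.025.

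**Step 1: dilution.** Per-case rate with no effect = p0/(1+k).

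| k | Severe | Mortality |
|---|---|---|
| 0 | 40% | 20% |
| 0.25 | 0.40/1.25 = 32% | 0.20/1.25 = 16% |
| 0.5 | 0.40/1.5 = 26.7% | 0.20/1.5 = 13.3% |
| 1 | 0.40/2 = 20% | 0.20/2 = 10% |

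**Step 2: chance of a false significant reduction.** Let c be the largest x with P(X ≤ x) ≤ 0.025 for X ~ Bin(n, p0). At n = 25/50/100, c = 4/12/30 for severe disease and 0/4/11 for death. The chance is P(X ≤ c) for X ~ Bin(n, p0/(1+k)).

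| k | Severe, n = 25 / 50 / 100 | Mortality, n = 25 / 50 / 100 |
|---|---|---|
| 0 | 0.9% / 1.3% / 2.5% | 0.4% / 1.8% / 1.3% |
| 0.25 | 6% / 14% / 38% | 1% / 8% / 11% |
| 0.5 | 16% / 40% / 81% | 3% / 19% / 30% |
| 1 | 42% / 81% / 99% | 7% / 43% / 70% |

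**Step 3: alternative set-up.** Fix the usually diagnosed cases at B = 25/50/100, so that n = B(1+k) and events ~ Bin(B, p0). For severe disease this gives 7%/16%/38% at k = 0.25, 27%/67%/94% at k = 0.5 and 85%/99.9%/about 100% at k = 1. The first set-up is the more cautious.

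**Step 4: few cases.** With n = 10, c = 0 for severe disease and the test rejects in 4.5% (k = 0.5) or 11% (k = 1). For mortality, even zero deaths cannot reach 0.025 at n = 16 or fewer (0.8^16 = 0.028). The point estimate is still biased: at k = 1 the observed severe rate is below 40% with probability 88% at n = 10, that is P(X ≤ 3) for Bin(10, 0.20), against 38% at k = 0.

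**Step 5: the other benchmark.** Against 10% severe, the no-effect rates of 32%, 26.7% and 20% all lie above the comparator, and the same test would show improvement in under 1% of trials at n = 25 to 100.

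**Step 6: a denominator that detection cannot enlarge.** Suppose 50 usually diagnosed cases: 50 × 40% = 20 severe. Per enrolled participant this is 20/500 = 4.0% for every k. Per case it is 20/50 = 40%, 20/75 = 26.7% and 20/100 = 20% for k = 0, 0.5 and 1.

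**The case against.** **The causal step is not in the documents.** A reader might infer that the app demonstrably adds mild infections. The text does not show that. An alert prompts contact and symptom assessment; no section says it leads to a COVID-19 test. A case enters when the participant presses a button in the app. The alert algorithm is in an appendix not available here, and neither usual-care testing nor detection in the published series is described. k could be near zero. This stands: the extra cases are likely, not established, and they would be mildly symptomatic rather than asymptomatic.

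**No test is planned.** Also true; the 0.025 test is an assumption. But the section D hypothesis speaks of significant improvement with no rule attached, and an informal reading of a lower rate has the same bias.

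**The comparison is exploratory.** Section A speaks of exploring a possible reduction and seeks R01 funding for the formal evaluation, and the Abstract leaves testing to later randomized trials. A reader might infer that the R01 case would rest on a false efficacy claim; the stated purpose of that grant does not support this. It limits the weight of the point, but the section D sentence remains stronger than the design allows.

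**The benchmark is open.** The section D sentence names no cancer-specific source, and the figures in the two tables do not carry over to the 10% overall rate. This stands.

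**The denominator is enhanced monitoring, not all cases.** Correct, and that group is described as non-emergent positives. The restriction does not offset the dilution: leaving out patients who are emergent at diagnosis would tend to lower the severe rate as well.

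**Conclusion.** The point holds as a caution on a secondary comparison. If the app brings in mild infections that usual care would miss, per-case severity and mortality would fall below the 40%/20% benchmark with no benefit to anyone, and nothing in the plan guards against reading that as improvement.

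Under the assumed test and 25 to 100 cases, the false-positive chance for severe disease runs from 6% (k = 0.25, 25 cases) to 99% (k = 1, 100 cases), and for mortality from 1% to 70%. The direction follows from the mechanism for any k above zero. The size depends on k, the case count, the test and the benchmark, none of which the plan fixes. With about 10 cases a formal test seldom rejects, though the estimate is still too low.

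A reader might go further and conclude that a false claim of benefit is the expected result of this trial, or that the study as a whole is compromised. The documents support neither: k is unknown, the conclusion fails against the 10% overall rate, and the primary feasibility aim does not use this comparison.

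**What to change.** 1. In section D (Study Design) and section M (Aim 2), with Aim 2b in section A aligned, replace the hypothesis of significant improvement with a descriptive estimate and confidence interval for each outcome. State that a per-case rate below published rates will not be read as benefit because ascertainment differs, and leave effect claims to the randomized trials foreseen in the Abstract.

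2. Also report COVID-19 hospitalizations and deaths per enrolled participant and per participant-month. Finding mild cases cannot dilute these rates. They depend on local incidence, so they are descriptive too.

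3. Route of detection may be tabulated where the record shows it, but cases found outside the app should not serve as an unbiased comparison group. Everyone is prompted daily, so such cases may be few and selected (missed prompts, acute presentation). The items listed in section E do not include the reason for testing.

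**Cost:** wording changes and a few table rows for items 1 and 2; no added patients or visits. The plan gives up the claim of improvement over the literature.

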RESEARCH PROTOCOL OUTLINE

Title of Project: Mobile Health Study and Enhanced Symptom Monitoring to Prevent Severe Illness from COVID-19 in Cancer Patients

Principal Investigators: [name]., Department of OB/GYN
[name], Dept. of Family and Preventive Medicine

Co-Investigators: [name], College of Public Health

Abstract

The severe acute respiratory syndrome corona virus 2 (SARS-CoV-2) outbreak in late 2019 has resulted in over 4.28 million confirmed cases of novel coronavirus disease (COVID-19), with over 292,000 confirmed deaths worldwide (as of May 13, 2020). Severe disease occurs in ~10% of cases overall. However, risk for severe disease and mortality is greater in immunocompromised cancer patients, requiring scarce ventilation resources and intensive care unit space to address rapid clinical deterioration in this population. We propose to use the established Insight™ mHealth Platform, a component of the Stephenson Cancer Center (SCC) mHealth Shared Resource, to create the “Symptom Tracker” app. The Symptom Tracker (Insight™) app will enable real-time monitoring of cancer patient symptoms that are consistent with early signs of SARS-CoV-2 infection in this high-risk population by automatically (and securely) transferring this information to health care providers. The primary aim of this study is to determine the feasibility, ease of use, and perceived utility of this app to monitor symptoms and health risk behaviors among cancer patients currently receiving chemotherapy. Health risk behaviors, standard COVID-19 screening questions, and a single chemotherapy risk question will be assessed daily through the smartphone app. Specific responses will automatically trigger an alert to clinic nurses AND provide app-based access to contact the clinic for triage to home care or emergency assessment. When/if study participants screen positive for COVID-19, they will receive a device to measure their pulse and blood oxygen levels daily. This information and COVID-19 symptoms will be monitored daily via the Symptom Tracker (Insight™) app. This study will determine if an app can be used to rapidly report COVID-19 symptoms and quickly intervene to reduce morbidity and mortality in immunocompromised cancer patients. Further, data from this study will be used to inform the development of future mHealth interventions that will be tested in fully powered randomized control trials.

A. Specific Aims

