All participants will be prompted to complete EMAs once per day during the 24-week study time period. If a participant contracts COVID-19, they will click the “COVID-19 Positive” button in the app. This action will cause the app to ask a different set of questions focused on enhanced monitoring COVID-19 symptoms for the next 21 days. At the end of 21 days, the app will return to daily prompts of the pre-COVID-19 EMAs. At the conclusion of the 24-week EMA period, participants will gain access to a new button in the app that will initiate the 24-week follow-up assessment (see Appendix). Participants will receive a daily alert from the app to click the “Final Survey” button in the app to complete the end of study assessment. The 24-week phone interview (or RedCap interview if a medical condition prevents them from being able to speak for long periods of time) will be scheduled at the baseline visit and the date/time of the call will appear at the top of the app home screen. A maximum of five phone call/text attempts and one mailed letter will occur over two-week period, before data from phone interview (or RedCap interview if a medical condition prevents them from being able to speak for long periods of time) will be considered unattainable. Those participants who were loaned a mobile phone to use during the study will be mailed a stamped envelope to return the phone and charger, or will be approached by study staff to reclaim the mobile device during a routine follow-up visit in the SCC chemo infusion clinic. Upon receipt of the smartphone and charging equipment, all equipment will be sterilized with alcohol-based sanitizer in accordance with current practice guidelines put forth by the Centers for Disease Control at the time it is returned by the study subject.

EMA completion rates, participant dropout, and feedback on the participant satisfaction survey will be used to evaluate feasibility of this type of mobile intervention in this population.

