This sample will consist of up to 500 male and female cancer patients. Individuals under the age of 18 (pediatric population) will be excluded from this study. Minorities will also be included, as this study seeks to adequately capture the diversity of patients receiving treatment at the SCC. There are no known additional risks for women or minorities.

J. Recruitment and Enrollment

Participants (N=500) will be recruited through the OU Medical Stephenson Cancer Center Infusion Clinic which is located at [name]. The SCC Infusion Clinic provides chemotherapy services for approximately 1200 patients per month. Based upon the treatment regimens provided, we anticipate that 250-300 cancer patients will be accrued to the trial every quarter. The clinic is staffed by oncologists, pharmacists, and advanced practice professionals. Patients will be given a verbal description of the study during a clinic visit, and those interested will be screened for study eligibility. Individuals who provide informed consent and meet the study inclusion criteria will complete the baseline assessment in the Infusion Clinic space. Participants will use study phones or personal smartphones to complete the baseline and follow-up assessment and phone-initiated and self-initiated surveys for the entire duration of the study. At the time of consent, patients will be provided with a copy of the informed consent to keep and will be encouraged to contact the investigators should they have further questions. The assessment questions are presented through the Insight™ mHealth platform. No incentive or cost reduction for care will be provided to the patient in order to minimize the risk of coercion. Several strategies will be utilized to retain study participants. Survey responses are automatically uploaded to the secure server every day; thus, study staff can closely monitor participant completion of daily surveys, and attempt to make contact with participants who do not complete them. Figure 1 displays the participant flow through the study.

K. Risks and Benefits

Participation in this study poses minimal risk to participants. Potential risks include consenting process and loss of confidentiality. Each of these risks are discussed below. The consent form will clearly describe the potential risks of this study. Thus, participants who feel uncomfortable with such assessments or intervention programs are not likely to agree to participate.

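### The COVID-19 outcome comparison with published rates has no calendar-period requirement, so any change in background severity over the roughly 11-month case window is confounded with the app

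*Combined protocol and SAP*

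**What the plan says.** The hypothesis stands in Section D, Study Design: enhanced monitoring will "significantly improve COVID-19 related morbidity and mortality compared to the national and international rates currently reported in the literature". The protocol's case and death counts (Abstract and Section B) carry the date May 13, 2020. The only cancer-specific benchmark is in Section B: "the risk of severe infection in cancer patients approaches 40% with up to a 20% mortality rate".

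Section A, Aim 2b, and Section M, Aim 2, both say the study will "compare rates of disease related morbidity and mortality to baseline rates published in the literature". Neither dates those rates nor names a source. Section A also plans exploratory comparisons of treatment initiation times and of symptom monitoring with published literature, again undated.

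Every participant receives the app, so there is no concurrent control. On timing, Section J says "Participants (N=500) will be recruited" and "we anticipate that 250-300 cancer patients will be accrued to the trial every quarter". Section D adds "All participants will be prompted to complete EMAs once per day during the 24-week study time period".

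Section M gives no test, significance level, null value, calendar window or adjustment for the external comparison. Its logistic regression and Kaplan-Meier analyses compare subgroups within the study.

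**The concern.** In a single-arm study the published rate is the only stand-in for what would have happened without the app. That works only if the published patients faced the same background severity as the study patients. The protocol itself describes the virus as novel and its effect on these patients as not fully understood, so it offers no basis for assuming that background severity stays fixed for close to a year.

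If the comparator comes from the first months of the pandemic and background severity then falls through changes in care, testing or the virus, the study shows a benefit that the app did not produce. If severity rises, a real benefit is hidden. This differs from the question of which patients and outcome definitions the comparator uses: a series with the right population and definitions would still mislead if it came from another period.

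The data are meant to support an application for further funding, so a misattributed mortality difference could travel beyond this study.

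**Working it through.** The documents state no total duration, significance level, power or case count, so there is no plan figure to reproduce.

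**1. Case window (from the documents)**

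- Accrual time = 500 / quarterly rate × 3 months. At 250 per quarter: 2 × 3 = 6.0 months. At 300 per quarter: 1.667 × 3 = 5.0 months.
- Follow-up of the last participant = 24 × 7 / 30.4375 = 5.5 months.
- Window = 6.0 + 5.5 = 11.5 months, or 5.0 + 5.5 = 10.5 months, from first enrolment.

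With uniform accrual over A months and no attrition, the share of follow-up in the first 3 months is (3² / 2) / A / 5.52. This is 0.136 for A = 6 and 0.163 for A = 5, so 84% to 86% of follow-up falls after month 3. No start date is given; a later start would widen the gap from May 2020.

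**2. Size of the biased contrast (drift assumed)**

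With no app effect, the apparent benefit equals the drift. A 25% relative fall turns 20% mortality into 15% (5 points) and 40% severe disease into 30% (10 points). A 50% fall gives 10 and 20 points. These contrasts do not depend on the number of cases.

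**3. Chance of a false improvement (illustration only)**

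Assumptions, none of them in the plan: an exact binomial test rejecting in the lower tail at 2.5%; null values borrowed from Section B (20% and 40%); no app effect; case counts of 20, 50 and 100. For each n, find the largest c with P(X ≤ c | n, p0) ≤ 0.025, then evaluate P(X ≤ c | n, p1) at the drifted rate p1.

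Mortality, p0 = 0.20:

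| Cases | c | No drift (0.20) | 25% fall (0.15) | 50% fall (0.10) |
|---|---|---|---|---|
| 20 | 0 | 0.012 | 0.04 | 0.12 |
| 50 | 4 | 0.018 | 0.11 | 0.43 |
| 100 | 11 | 0.013 | 0.16 | 0.70 |

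Below 17 cases the mortality test cannot reject even with no deaths: 0.8^16 = 0.028 exceeds 0.025, while 0.8^17 = 0.0225 does not.

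Severe disease, p0 = 0.40:

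| Cases | c | No drift (0.40) | 25% fall (0.30) | 50% fall (0.20) |
|---|---|---|---|---|
| 20 | 3 | 0.016 | 0.11 | 0.41 |
| 50 | 12 | 0.013 | 0.22 | 0.81 |
| 100 | 30 | 0.025 | 0.55 | 0.99 |

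More cases make the error more likely, because a larger sample estimates the wrong contrast more precisely.

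**The case against.** A reader might infer that the plan freezes its comparator at May 2020 and that every study case therefore postdates it. The documents do not go that far. That reading joins one adverb in the Section D hypothesis to the date of the general case counts. Sections A and M, which describe the comparison itself, leave the published rates undated, so literature available at analysis is allowed. What stands is that nothing requires it, and the one phrase that points to a period points to the time of writing.

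A reader might also infer that a formal test of mortality is planned. It is not. Section A speaks of exploring a potential reduction, the primary aim is feasibility, and the Abstract leaves effectiveness to later randomized trials. A literature benchmark is an ordinary limitation of a secondary aim in such a study. Even so, the Section D wording on significant improvement invites a test and a causal reading, and nothing in Section M restrains either.

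The illustration rests on supplied assumptions. The 20% (given as an upper figure) and the 40% are background figures and are never designated as null values. The documents give no COVID-19 incidence and no evidence of drift or its direction. With few cases a false significant result is unlikely or impossible. This limits the error rates but does not remove the bias in the point comparison.

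Finally, the funding application is described as the place where effects would be formally evaluated; the text does not say that the mortality comparison is its basis.

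**Conclusion.** The point holds as a gap in the plan: the external comparison has no calendar-period requirement, cases arise over about 10.5 to 11.5 months from first enrolment, and nothing planned separates an app effect from a change in background severity. The window follows from the plan's own figures, assuming the stated accrual rate is met.

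The size of any bias is unknown. Under an assumed 25% relative fall it is 5 points for mortality and 10 points for severe disease at any case count. Under the assumed test, the chance of a false improvement is then 0.04, 0.11 and 0.16 for mortality, and 0.11, 0.22 and 0.55 for severe disease, at 20, 50 and 100 cases. Drift in the other direction would mask a benefit. The feasibility aim is untouched. The change is worth making because it is cheap and the present wording invites a claim that the design cannot support.

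**What to change.** - In Section D (hypothesis), Section A (Aim 2b) and Section M (Aim 2), replace the references to current and baseline rates with published rates for cancer patients diagnosed over the same overall calendar period as the study cases, taken from the literature available at analysis.
- Delete 'significantly' from the Section D hypothesis. State that the comparison is descriptive and does not support attributing a difference to the app.
- Report study rates with confidence intervals and list cases and outcomes by calendar period. Standardizing quarter by quarter is not needed: an assumed 50 cases over about four quarters leaves 50 / 4 = 12.5 cases per quarter, or 2.5 deaths at 20%.
- If no calendar-matched series exists, report the study rates with confidence intervals only.

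The cost is wording in three sections and a literature search at analysis. The comparator value will not be known until then. App entries are time-stamped, but the positive-test button records when the participant clicked, not when the diagnosis was made, so diagnosis dates may need checking against the health record.
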